**Table 2-3: On-Treatment - Schedule of Activities for Q2W Dosing Schedules in BMS-986218 Monotherapy Escalation (Part 1A)**

Procedure	Cycle 1 (28 Days in Length) (Visit Window $\pm$ 2 Days, except for C1D1)				Cycle 2 (28 Days in Length) (Visit Window $\pm$ 2 Days)				Cycles 3 and Beyond (Each Cycle 28 Days in Length) (Visit Window $\pm$ 2 Days)	EOT a,b	Notes			
	DLT Period is Cycles 1 and 2													
	D1	D8	D15	D22	D1	D8	D15	D22	D1 & D15					
Urinalysis	X		X		X		X		As clinically indicated; microscopic urine reflex only for urinalysis positive for blood/protein/ leukocyte esterase	X				
Pregnancy Test (WOCBP only)	X				X				X (Day 1 only)	X	Serum/urine for pregnancy test to be collected within 24 hours prior to dosing on Day 1 of each cycle. Pregnancy test may be completed on the first day of treatment, provided the results are available before the start of study therapy. Serum or urine pregnancy test must be performed within 24 hours prior to administration of study treatment on Day 1 of each cycle (urine pregnancy test: minimum sensitivity 25 IU/L or equivalent units of hCG).			

**Table 2-3: On-Treatment - Schedule of Activities for Q2W Dosing Schedules in BMS-986218 Monotherapy Escalation (Part 1A)**

Procedure	Cycle 1 (28 Days in Length) (Visit Window $\pm$ 2 Days, except for C1D1)				Cycle 2 (28 Days in Length) (Visit Window $\pm$ 2 Days)				Cycles 3 and Beyond (Each Cycle 28 Days in Length) (Visit Window $\pm$ 2 Days)	EOT a,b	Notes			
	DLT Period is Cycles 1 and 2													
	D1	D8	D15	D22	D1	D8	D15	D22	D1 & D15					
Adverse Event Reporting and Concomitant Medication Assessments														
Monitor for Non-SAEs	Non-SAEs will be collected starting with the first dose of study medication and through 100 days following the last dose of study treatment.										Section 9.2 and Appendix 3. All AEs (SAEs or nonserious AEs) including those associated with SARS-CoV-2 infection must be collected continuously during the treatment period.			
Monitor for SAEs	All SAEs must be collected from the date of the participant's written consent until 100 days following the last dose of study treatment.										Section 9.2 and Appendix 3.			
Concomitant Medications	X	X	X	X	X	X	X	X	X					
PK Assessments														
Serial Blood Sampling	See Table 9.5-3 of the PK and immunogenicity sampling schedule and Section 9.5.													
Immunogenicity (ADA) Assessments	See Table 9.5-3 of the PK and immunogenicity sampling schedule and Section 9.5.													

**Table 2-3: On-Treatment - Schedule of Activities for Q2W Dosing Schedules in BMS-986218 Monotherapy Escalation (Part 1A)**

Procedure	Cycle 1 (28 Days in Length) (Visit Window $\pm$ 2 Days, except for C1D1)				Cycle 2 (28 Days in Length) (Visit Window $\pm$ 2 Days)				Cycles 3 and Beyond (Each Cycle 28 Days in Length) (Visit Window $\pm$ 2 Days)	EOT a,b	Notes			
	DLT Period is Cycles 1 and 2													
	D1	D8	D15	D22	D1	D8	D15	D22	D1 & D15					
Imaging Assessments														
Body Imaging	Tumor imaging assessment to be performed Q8W from the first dose ( $\pm$ 1 week), prior to initiating next cycle of treatment in Part 1A. Participants who remain free of subsequent therapy will undergo tumor imaging assessment Q8W ( $\pm$ 1 week) until subsequent tumor-directed therapy is initiated or until 48 weeks after discontinuation of study treatment/EOT visit, and then Q12W ( $\pm$ 2 weeks) for a total duration of 2 years.													
Brain Imaging	Participants with history of brain metastasis will have MRI performed as clinically indicated and at the discretion of the Investigator.													

**Table 2-3: On-Treatment - Schedule of Activities for Q2W Dosing Schedules in BMS-986218 Monotherapy Escalation (Part 1A)**

Procedure	Cycle 1 (28 Days in Length) (Visit Window $\pm$ 2 Days, except for C1D1)				Cycle 2 (28 Days in Length) (Visit Window $\pm$ 2 Days)				Cycles 3 and Beyond (Each Cycle 28 Days in Length) (Visit Window $\pm$ 2 Days)	EOT a,b	Notes				
	DLT Period is Cycles 1 and 2														
	D1	D8	D15	D22	D1	D8	D15	D22							

**Table 2-3: On-Treatment - Schedule of Activities for Q2W Dosing Schedules in BMS-986218 Monotherapy Escalation (Part 1A)**

Procedure	Cycle 1 (28 Days in Length) (Visit Window $\pm$ 2 Days, except for C1D1)				Cycle 2 (28 Days in Length) (Visit Window $\pm$ 2 Days)				Cycles 3 and Beyond (Each Cycle 28 Days in Length) (Visit Window $\pm$ 2 Days)	EOT a,b	Notes				
	DLT Period is Cycles 1 and 2														
	D1	D8	D15	D22	D1	D8	D15	D22							
Clinical Treatment Supplies															
BMS-986218 Administration	X		X		X		X		X			Study treatment, BMS-986218, to be supplied by BMS; vials assigned by IRT must be used.			

Abbreviations: ADA = anti-drug antibody; AE = adverse event; BMS = Bristol-Myers Squibb; CXDY = Cycle X Day Y, as an example; CT = computed tomography; D = day; DLT = dose-limiting toxicity; ECG = electrocardiogram; ECOG = Eastern Cooperative Oncology Group; EOI = end of infusion; hCG = human chorionic gonadotropin; [REDACTED] IRT = Interactive Response Technology; MRI = magnetic resonance imaging; PCWG 3 = Prostate Cancer Working Group 3; PE = physical examination; PK = pharmacokinetic; Q8W = every 8 weeks; Q12W = every 12 weeks;

RECIST = Response Evaluation Criteria in Solid Tumors; SAE = serious adverse event; SARS-CoV-2 = severe acute respiratory syndrome coronavirus 2; WOCBP = women of childbearing potential.

- a EOT is defined as the visit where the decision is made to discontinue the participant from treatment. Evaluations will be performed prior to study discharge, or for participants who are prematurely discontinued.
- b For participants who complete all scheduled cycles of therapy, the EOT visit will be the same as the last scheduled and completed on-treatment visit (eg, Cycle 3 Day 21) and the start of the Safety Follow-up Period. For participants who do not complete all scheduled cycles of therapy, the EOT visit will be the most recent on-treatment visit (with all available safety and response data); it does not need to be repeated and will be considered as the start of the Safety Follow-up Period.

**Table 2-4: On-Treatment - Schedule of Activities for Q3W Dosing Schedule for Ipilimumab in the Randomized BMS-986218 Monotherapy Cohort Expansion in Cutaneous Melanoma (Part 2A)**

Procedure	Cycle 1 (21 Days in Length) (Visit Window $\pm$ 2 Days, except for C1D1)			Cycle 2 (21 Days in Length) (Visit Window $\pm$ 2 Days)			Cycle 3 and Cycle 4 (21 Days in Length) (Visit Window $\pm$ 2 Days)			EOT a,b	Notes
	D1	D8	D15	D1	D8	D15	D1	D8	D15		
Safety Assessments											
ECOG Performance Status	X			X			X			X	
PE	X			X			X			X	
Symptom Directed PE		X	X		X	X					
Weight	X			X			X			X	
Vital Signs	X	X	X	X	X	X	X			X	For ipilimumab, vital signs will be obtained within 30 minutes before the start of the infusion and then every 30 minutes ( $\pm$ 5 minutes) from the start of the infusion until completion of the infusion. If any vital sign is abnormal (based upon clinician assessment) at the final check, the participant must be observed further for a period, as clinically indicated.
Oxygen Saturation	X			X			X				
ECG	X			X			X			X	ECGs should be recorded after the participant has been supine for at least 5 minutes and prior to blood draws. Single safety ECGs to be done prior to each infusion for all treatment cycles. ECGs must be performed on Day 1 of each cycle and at EOT.

**Table 2-4: On-Treatment - Schedule of Activities for Q3W Dosing Schedule for Ipilimumab in the Randomized BMS-986218 Monotherapy Cohort Expansion in Cutaneous Melanoma (Part 2A)**

Procedure	Cycle 1 (21 Days in Length) (Visit Window $\pm$ 2 Days, except for C1D1)			Cycle 2 (21 Days in Length) (Visit Window $\pm$ 2 Days)			Cycle 3 and Cycle 4 (21 Days in Length) (Visit Window $\pm$ 2 Days)			EOT a,b	Notes
	D1	D8	D15	D1	D8	D15	D1	D8	D15		
Laboratory Tests	X	X	X	X	X	X	X			X	There will be a minus-72-hour window for collection of laboratory tests on Day 1 of each cycle and a window of $\pm$ 2 days window for all other timepoints. Coagulation assessments will be performed at screening only. See Section 9.1.4 and Table 9.1.4-1 .
Urinalysis	X			X			As clinically indicated; microscopic urine reflex only for urinalysis positive for blood/protein/leukocyte esterase.		X		
Pregnancy Test (WOCBP only)	X			X			X		X	Serum/urine to be collected within 24 hours prior to dosing. Pregnancy test may be completed on the first day of treatment, provided the results are available before the start of study therapy. Serum or urine pregnancy test must be performed within 24 hours prior to administration of study treatment (urine pregnancy test: minimum sensitivity 25 IU/L or equivalent units of hCG).	

**Table 2-4: On-Treatment - Schedule of Activities for Q3W Dosing Schedule for Ipilimumab in the Randomized BMS-986218 Monotherapy Cohort Expansion in Cutaneous Melanoma (Part 2A)**

Procedure	Cycle 1 (21 Days in Length) (Visit Window $\pm$ 2 Days, except for C1D1)			Cycle 2 (21 Days in Length) (Visit Window $\pm$ 2 Days)			Cycle 3 and Cycle 4 (21 Days in Length) (Visit Window $\pm$ 2 Days)			EOT a,b	Notes
	D1	D8	D15	D1	D8	D15	D1	D8	D15		
Adverse Event Reporting and Concomitant Medication Assessments											
Monitor for Non-SAEs	Non-SAEs will be collected starting with the first dose of study medication and through 100 days following last dose of study treatment.									Section 9.2 and Appendix 3.	All AEs (SAEs or nonserious AEs) including those associated with SARS-CoV-2 infection must be collected continuously during the treatment period
Monitor for SAEs	All SAEs must be collected from the date of the participant's written consent until 100 days following the last dose of study treatment.									Section 9.2 and Appendix 3.	
Concomitant Medications	X	X	X	X	X	X	X	X			
PK Assessments											
Serial Blood Sampling	See Table 9.5-4 of the PK and immunogenicity sampling schedule and Section 9.5.										
Immunogenicity (ADA) Assessments	See Table 9.5-4 of the PK and immunogenicity sampling schedule and Section 9.5.										
Imaging Assessments											
Body Imaging	Tumor imaging assessment to be performed at 12 weeks from the first dose, regardless of dose delays, if any ( $\pm$ 1 week). After that, subsequent tumor imaging assessments to be performed Q8W ( $\pm$ 1 week). Participants who remain free of subsequent therapy will undergo tumor imaging assessment Q8W ( $\pm$ 1 week) until subsequent tumor-directed therapy is initiated or until 48 weeks after discontinuation of study treatment/EOT visit, and then Q12W ( $\pm$ 2 weeks) for a total duration of 2 years.									The same imaging modality is to be used for all assessments, per RECIST v1.1 (Appendix 5). CT and MRI scans should be acquired with slice thickness of 5 mm or less with no intervening gap (contiguous). Every attempt should be made to image each participant using an identical acquisition protocol on the same scanner for all imaging timepoints.	

**Table 2-4: On-Treatment - Schedule of Activities for Q3W Dosing Schedule for Ipilimumab in the Randomized BMS-986218 Monotherapy Cohort Expansion in Cutaneous Melanoma (Part 2A)**

Procedure	Cycle 1 (21 Days in Length) (Visit Window $\pm$ 2 Days, except for C1D1)			Cycle 2 (21 Days in Length) (Visit Window $\pm$ 2 Days)			Cycle 3 and Cycle 4 (21 Days in Length) (Visit Window $\pm$ 2 Days)			EOT a,b	Notes
	D1	D8	D15	D1	D8	D15	D1	D8	D15		
Brain Imaging	Participants with history of brain metastasis will have MRI performed as clinically indicated and at the discretion of the Investigator.									MRI without and with contrast of the brain should be performed. CT of the brain without and with contrast may be obtained if MRI is contraindicated. CT and MRI scans should be acquired with slice thickness of 5 mm or less with no intervening gap (contiguous). Every attempt should be made to image each participant using an identical acquisition protocol on the same scanner for all imaging timepoints.	

**Table 2-4: On-Treatment - Schedule of Activities for Q3W Dosing Schedule for Ipilimumab in the Randomized BMS-986218 Monotherapy Cohort Expansion in Cutaneous Melanoma (Part 2A)**

Procedure	Cycle 1 (21 Days in Length) (Visit Window $\pm$ 2 Days, except for C1D1)			Cycle 2 (21 Days in Length) (Visit Window $\pm$ 2 Days)			Cycle 3 and Cycle 4 (21 Days in Length) (Visit Window $\pm$ 2 Days)			EOT a,b	Notes
	D1	D8	D15	D1	D8	D15	D1	D8	D15		

**Table 2-4: On-Treatment - Schedule of Activities for Q3W Dosing Schedule for Ipilimumab in the Randomized BMS-986218 Monotherapy Cohort Expansion in Cutaneous Melanoma (Part 2A)**

Procedure	Cycle 1 (21 Days in Length) (Visit Window $\pm$ 2 Days, except for C1D1)			Cycle 2 (21 Days in Length) (Visit Window $\pm$ 2 Days)			Cycle 3 and Cycle 4 (21 Days in Length) (Visit Window $\pm$ 2 Days)			EOT a,b	Notes
	D1	D8	D15	D1	D8	D15	D1	D8	D15		
Clinical Treatment Supplies											
Ipilimumab Administration	X			X			C3 and C4 only				Ipilimumab to be administered for up to a maximum of 4 doses. Ipilimumab study treatment to be supplied by BMS; vials assigned by IRT must be used.

Abbreviations: ADA = anti-drug antibody; AE = adverse event; BICR = blinded independent central review; C = cycle; CXDY = Cycle X Day Y, as an example; D = day; DLT = dose-limiting toxicity; ECG = electrocardiogram; [REDACTED] EOT = end of treatment; [REDACTED]

[REDACTED] hCG = human chorionic gonadotropin; [REDACTED] IRT = Interactive Response Technology; MRI = magnetic resonance imaging; PCWG 3 = Prostate Cancer Working Group 3; PE = physical examination; PK = pharmacokinetic; [REDACTED] Q8W = every 8 weeks; Q12W = every 12 weeks; RECIST = Response Evaluation Criteria in Solid Tumors; SAE = serious adverse event; SARS-CoV-2 = severe acute respiratory syndrome coronavirus 2.

a EOT is defined as the visit where the decision is made to discontinue the participant from treatment. Evaluations will be performed prior to study discharge, or for participants who are prematurely discontinued.

b For participants who complete all scheduled cycles of therapy, the EOT visit will be the same as the last scheduled and completed on-treatment visit (eg, Cycle 4 Day 21) and the start of the Safety Follow-up Period. For participants who do not complete all scheduled cycles of therapy, the EOT visit will be the most recent on-treatment visit (with all available safety and response data); it does not need to be repeated and will be considered the start of the Safety Follow-up Period.

**Table 2-5: Follow-up Procedural Outline for All Study Parts (CA022001)**

Procedure	Safety Follow-up			Response Follow-up	Survival Follow-up b	Notes
	Follow-up 1 30 Days a (± 7 Days)	Follow-up 2 60 Days (± 7 Days)	Follow-up 3 100 Days (± 7 Days)			
Safety Assessments						
PE	X	X	X			
Vital Signs	X	X	X			Includes body temperature, seated/supine blood pressure, and heart rate.
Laboratory Tests	X	X	X			Laboratory tests also as clinically indicated; See laboratory assessments in Section 9.1.4 and Table 9.1.4-1 .
Urinalysis	As clinically indicated (see Section 9.1.4).					
Pregnancy Test	X	X	X			For WOCBP, serum/urine pregnancy test is to be performed (urine pregnancy test: minimum sensitivity 25 IU/L or equivalent units of hCG) (see Section 9.2.5 ). For additional country-local requirements, refer to Appendix 8 .
Adverse Event Reporting and Concomitant Medication Assessments						
Monitor for Non-SAEs	X	X	X			Non-serious AEs will be collected starting with the first dose of study medication and through 100 days after discontinuation of dosing ( Section 9.2 and Appendix 3 ). Participants will be followed for all SAEs, and all AEs (SAEs and non-serious AEs) associated with confirmed or suspected SARS-CoV-2 infection until resolution, the condition stabilizes, the event is otherwise explained, the event is deemed irreversible, the participant is lost to follow-up (as defined in Section 8.3 ), or for suspected cases, until SARS-CoV-2 infection is ruled-out.

**Table 2-5: Follow-up Procedural Outline for All Study Parts (CA022001)**

Procedure	Safety Follow-up			Response Follow-up	Survival Follow-up b	Notes
	Follow-up 1 30 Days a (± 7 Days)	Follow-up 2 60 Days (± 7 Days)	Follow-up 3 100 Days (± 7 Days)			
Monitor for SAEs	X	X	X			All SAEs must be collected from the date of the participant's written consent until 100 days after discontinuation of dosing.  Participants will be followed for all SAEs, non-serious AEs of special interest (as defined in Section 9.2.3 ), and all AEs (SAEs and non-serious AEs) associated with confirmed or suspected SARS-CoV-2 infection until resolution, the condition stabilizes, the event is otherwise explained, the event is deemed irreversible, the participant is lost to follow-up (as defined in Section 8.3 ), or for suspected cases, until SARS-CoV-2 infection is ruled-out.
Concomitant Medication Assessments	X	X	X			
Sample Collection						
PK Assessments	See Table 9.5-2 , Table 9.5-3 , Table 9.5-4 , and Table 9.5-5 of the PK and immunogenicity sampling schedule and Section 9.5 .					
Immunogenicity (ADA) Assessments	See Table 9.5-2, Table 9.5-3, Table 9.5-4, and Table 9.5-5 of the PK and immunogenicity sampling schedule and Section 9.5.					
Efficacy Assessments						

**Table 2-5: Follow-up Procedural Outline for All Study Parts (CA022001)**

Procedure	Safety Follow-up			Response Follow-up	Survival Follow-up b	Notes
	Follow-up 1 30 Days a (± 7 Days)	Follow-up 2 60 Days (± 7 Days)	Follow-up 3 100 Days (± 7 Days)			
Tumor/Response Assessments				X		
At the time of the EOT visit or at the time of study treatment discontinuation, all participants will continue to have radiologic and clinical tumor assessments every Q8W (± 1 week) until subsequent tumor-directed therapy is initiated or until 48 weeks after discontinuation of study treatment/EOT visit, and then Q12W (± 2 weeks) for a total duration of 2 years. Radiologic assessments for participants who have ongoing clinical benefit and remain free of subsequent therapy may continue to be collected after participants complete the Survival Follow-up Period of the study. Scans will be submitted to an imaging core laboratory for review by BICR at a later date, or at any time during the study at the Sponsor's discretion.
 
CT and MRI scans should be acquired with slice thickness of 5 mm or less with no intervening gap (contiguous). Every attempt should be made to image each participant using an identical acquisition protocol on the same scanner for all imaging timepoints.

Brain Imaging				X		
As clinically indicated, CT and MRI scans should be acquired with slice thickness of 5 mm or less with no intervening gap (contiguous). Every attempt should be made to image each participant using an identical acquisition protocol on the same scanner for all imaging timepoints.

Bone Scan				X		
Required for participants with prostate cancer for evaluation of bone disease; otherwise, as clinically indicated. Every attempt should be made to image each participant using an identical acquisition protocol on the same scanner for all imaging timepoints.

**Table 2-5: Follow-up Procedural Outline for All Study Parts (CA022001)**

Procedure	Safety Follow-up			Response Follow-up	Survival Follow-up b	Notes
	Follow-up 1 30 Days a (± 7 Days)	Follow-up 2 60 Days (± 7 Days)	Follow-up 3 100 Days (± 7 Days)			
Subsequent Treatments (Anti-cancer)	X	X	X		X	
Assessment of Participant Survival Status					X	Participant status will be assessed by any documented clinic visit or telephone contact Q12W.

Abbreviations: ADA = anti-drug antibody; AE = adverse event; BICR = blinded independent central review; CR = complete response; EOT = end of treatment; [REDACTED] EOT = end of treatment; [REDACTED] hCG = human chorionic gonadotropin; [REDACTED]  
 [REDACTED] PE = physical examination; PR = partial response; PK = pharmacokinetics; [REDACTED]  
 [REDACTED] Q8W = every 8 weeks; Q12W = every 12 weeks; SAE = serious adverse event; SARS-CoV-2 = severe acute respiratory syndrome coronavirus 2; SD = stable disease; WOCBP = women of child bearing potential.

a Follow-up visits at Days 30 (± 7 days), 60 (± 7 days), and 100 (± 7 days) should occur relative to the last dose of study treatment or date of discontinuation, whichever is later.

b Survival Follow-up will be measured Q12W (± 2 weeks) for up to 4 years from the date of the first dose of study treatment.

In the event that multiple procedures are required at a single time point, the electrocardiogram (ECG) may be obtained up to 15 minutes earlier, vital signs may be obtained up to 10 minutes earlier or later, and clinical laboratory sample may be obtained up to 5 minutes earlier than the nominal timepoint, ensuring that the pharmacokinetics (PK) samples can be collected on time.

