**Table 2-2:**

**On-Treatment - Schedule of Activities for Q4W Dosing Schedules in BMS-986218 Monotherapy Escalation (Part 1A), Safety Evaluation of Combination Doses of BMS-986218 with Nivolumab (Part 1B), Randomized BMS-986218 Monotherapy Cohort Expansion in Cutaneous Melanoma (Part 2A), Randomized BMS-986218 Monotherapy Cohort Expansion (Part 2B), and Combination Cohort Expansions (Part 2C and Part 2D)**

Procedure	Cycle 1 (28 Days in Length) (Visit Window $\pm$ 2 Days, except for C1D1)				Cycle 2 (28 Days in Length) (Visit Window $\pm$ 2 Days)				Cycles 3 and Beyond (Each Cycle 28 Days in Length) (Visit Window $\pm$ 2 Days)	EOT a,b	Notes			
	DLT Period is Cycles 1 and 2													
	D1	D8	D15	D22	D1	D8	D15	D22	D1					
												of the infusion until completion of the infusion.  If any vital sign is abnormal (based upon clinician assessment) at the final check, the participant must be observed further for a period of time, as clinically indicated.		
Oxygen Saturation	X				X				X			Oxygen saturation to also be performed in conjunction with vital signs monitoring on these days. For all cycles after Cycle 3, vital signs and oxygen saturation are to be taken before the infusion and at the end of each infusion.		
ECG	X				X				X	X		ECGs should be recorded after the participant has been supine for at least 5 minutes and prior to blood draws. ECGs to be performed in triplicate in association with PK sampling, at predose and EOI, on Day 1 of both Cycle 1 and Cycle 3 for Part 1A only (see Section 9.1.3 ). Single safety ECGs to be performed for all other time points.		

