**Table 2-3: On-Treatment - Schedule of Activities for Q2W Dosing Schedules in BMS-986218 Monotherapy Escalation (Part 1A)**

Procedure	Cycle 1 (28 Days in Length) (Visit Window $\pm$ 2 Days, except for C1D1)				Cycle 2 (28 Days in Length) (Visit Window $\pm$ 2 Days)				Cycles 3 and Beyond (Each Cycle 28 Days in Length) (Visit Window $\pm$ 2 Days)	EOT a,b	Notes			
	DLT Period is Cycles 1 and 2													
	D1	D8	D15	D22	D1	D8	D15	D22	D1 & D15					
Oxygen Saturation	X		X		X		X		X			Oxygen saturation to also be performed in conjunction with vital signs monitoring on these days. For all infusions after C2D1, vital signs and oxygen saturation are to be taken before the infusion and at the end of each infusion.		
ECG		X		X		X		X		X		ECGs should be recorded after the participant has been supine for at least 5 minutes and prior to blood draws. ECGs to be performed in triplicate in association with PK sampling, at predose and EOI, on Day 1 of both Cycle 1 and Cycle 3 for Part 1A only (see Section 9.1.3 ). Single safety ECGs to be performed for all other time points. Beyond Cycle 3, ECGs must be performed every 3 cycles up to EOT.		
Laboratory Tests	X	X	X	X	X	X	X	X	X	X		There will be a minus-72-hour window for collection of laboratory tests on Day 1 of each cycle and a window of $\pm$ 2 days for all other timepoints. Coagulation assessment at screening only. See Section 9.1.4 and Table 9.1.4-1 .		

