Weekly study visits will be performed for the first 8 weeks following the first dose of study treatment for the BMS-986218 Monotherapy Escalation (Part 1A), Safety Evaluation of Combination Doses of BMS-986218 with Nivolumab (Part 1B), the Randomized BMS-986218 Monotherapy Cohort Expansion in Cutaneous Melanoma (Part 2A), the Randomized BMS-986218 Monotherapy Cohort Expansion (Part 2B), the BMS-986218 Combination Therapy Cohort Expansion in NSCLC (Part 2C) and the BMS-986218 Combination Therapy Cohort Expansion in microsatellite stable colorectal cancer (MSS CRC) (Part 2D) followed by study visits Q4W thereafter. During Cycle 1 and Cycle 3 of the treatment period, additional study visits to collect samples for intensive PK, ADA, and cytokine assessments are required. See [Section 9.5](#) for further details.

In the BMS-986218 Monotherapy Escalation (Part 1A), the Randomized BMS-986218 Monotherapy Cohort Expansion in Cutaneous Melanoma (Part 2A), and the Randomized BMS-986218 Monotherapy Cohort Expansion (Part 2B), BMS-986218 will be administered Q4W. An alternative BMS-986218 dosing schedule of Q2W (with dosing on Day 1 and Day 15 of each 28-day cycle) will also be explored for monotherapy escalation using data obtained from the Q4W schedule. BMS-986218 will be infused over 30 minutes, except in the low-dose cohorts where infusion times may be shorter. BMS-986218 will require a 60-minute observation period following the completion of the infusion for the first 3 doses for each participant. Ipilimumab will be administered Q3W and will be infused over 30 minutes.

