**Table 7.3-1: Selection and Timing of Dose for All Study Parts**

Study Treatment	Flat Dose Levels	Frequency of Administration	Route of Administration	Infusion Time (Minutes)
BMS-986218	2, 4, 7, 20, 40, 70, 100, 150 or 200 mg	Q4W	IV	Doses administered over approximately 30 minutes.
BMS-986218	10, 20, 35, 50, 75 or 100 mg	Q2W	IV	Doses administered over approximately 30 minutes.
Ipilimumab	3 mg/kg a	Q3W (up to a maximum of 4 doses)	IV	Approximately 30 minutes
Nivolumab	480 mg	Q4W b	IV	Approximately 30 minutes

a Dosing calculations should be based on the body weight assessed at Cycle 1 Day 1 prior to the first dose of ipilimumab. If the participant's weight on the day of dosing differs by > 10% from the weight used to calculate the prior dose, the dose must be recalculated.

b For participants in the Safety Evaluation of Combination Doses of BMS-986218 with Nivolumab (Part 1B) and the BMS-986218 Cohort Expansion - Combination Therapy (Part 2C and Part 2D), a 30-minute infusion of nivolumab will be followed by a 30-minute observation period, followed by a 30-minute infusion of BMS-986218 and a 60-minute observation period following the first 3 infusions for each participant.

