### **9.1.3 *Electrocardiograms***

Refer to the Schedule of Activities for timing of assessments in [Table 2-1](#), [Table 2-2](#), [Table 2-3](#), and [Table 2-4](#).

The effect of BMS-986218 on the QTc interval will be evaluated by a central reader using ECG data collected in triplicate along with time-matched PK during the BMS-986218 Monotherapy Dose Escalation (Part 1A) only (eg, 1 ECG test equals 3 consecutive individual 12-lead ECGs performed 5 minutes apart). For the purposes of monitoring participant safety, the Investigators will review the 12-lead ECGs using their site's standard ECG machines throughout the study. The QTcF will be applied to each ECG reading.

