Study Day of Sample Collection (1 cycle = 4 weeks)	Event	Time (relative to initiation of BMS-986218 dose) Hour:Minute	BMS-986218 Blood Sample	BMS-986218 ADA Samples
C1D1	Predose a	00:00	X	X
	EOI	See note b	X	
C1D2		24:00	X	
C1D8 c		168:00	X	
C1D15 c		336:00	X	
C1D22 c		504:00	X	
C2D1	Predose a	00:00	X	X
	EOI	See note b	X	
C2D8 c		168:00	X	
C3D1	Predose a	00:00	X	X
	EOI	See note b	X	
C3D2		24:00	X	
C3D8 c		168:00	X	
C3D15 c		336:00	X	
C3D22 c		504:00	X	
C4D1	Predose a	00:00	X	X
C5D1	Predose a	00:00	X	X

**Table 9.5-2: Pharmacokinetic and Anti-Drug Antibody (ADA) Sampling Schedule for BMS-986218 Q4W Monotherapy in Dose Escalation (Part 1A) and Dose Expansion (Part 2A and Part 2B)**

Study Day of Sample Collection (1 cycle = 4 weeks)	Event	Time (relative to initiation of BMS-986218 dose) Hour:Minute	BMS-986218 Blood Sample	BMS-986218 ADA Samples
Every fourth cycle after C5 until EOT (C9D1, C13D1, C17D1, etc. until EOT)	Predose a	00:00	X	X
EOT			X	X
30-day follow-up			X	X
60-day follow-up			X	X
100-day follow-up			X	X
Grade 3+ Infusion Reaction			X	X

a Predose: All predose samples should be taken prior to the start of the infusion.

b EOI PK should be collected when all the study drug has been infused. If a flush is administered to clear the IV lines of the drug and to ensure delivery of the entire drug dose, then draw the EOI PK sample within approximately 15 minutes after end of the flush. Do not draw EOI samples from the same IV access that the drug was administered. Refer to [Table 7.3-1](#) for infusion duration. If the EOI is delayed to beyond the nominal infusion duration, the collection of this sample should also be delayed accordingly.

c This sample may be collected  $\pm$  2 days from timepoint. The actual date and time of sampling must be recorded.

Abbreviations: C = cycle; D = day; EOI = end of infusion; IV = intravenous; PK = pharmacokinetic.

**Table 9.5-3:** **Pharmacokinetic and Anti-Drug Antibody (ADA) Sampling Schedule for BMS-986218 Q2W Monotherapy in Dose Escalation (Part 1A)**

Study Day of Sample Collection (1 cycle = 4 weeks)	Event	Time (relative to initiation of BMS-986218 dose) Hour:Minute	BMS-986218 Blood Sample	BMS-986218 ADA Samples
C1D1	Predose a	00:00	X	X
	EOI	See note b	X	
C1D2		24:00	X	

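### The 15-minute-early ECG tolerance has no end-of-infusion exception, so Part 1A QTc triplicates may be recorded mid-infusion yet paired with a post-infusion concentration

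*Combined protocol and SAP*

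**What the plan says.** - **Tolerance (text after Table 2-5).** Where several procedures fall at one time point, "the electrocardiogram (ECG) may be obtained up to 15 minutes earlier, vital signs may be obtained up to 10 minutes earlier or later", counted from the nominal time. The stated aim is "ensuring that the pharmacokinetics (PK) samples can be collected on time". The rule is permissive and names no exception for EOI or for the QTc triplicates.
- **QTc time points (ECG notes, Tables 2-2 and 2-3).** "ECGs to be performed in triplicate in association with PK sampling, at predose and EOI", on Day 1 of Cycles 1 and 3, Part 1A only. Also: "ECGs should be recorded after the participant has been supine for at least 5 minutes and prior to blood draws".
- **QTc evaluation (Section 9.1.3).** A central reader evaluates QTc "using ECG data collected in triplicate along with time-matched PK". One test is three ECGs taken 5 minutes apart.
- **Infusion time.** Table 7.3-1, for every Q4W and Q2W dose level: "Doses administered over approximately 30 minutes". Section 5.1.2 also gives 30 minutes, but "except in the low-dose cohorts where infusion times may be shorter".
- **EOI PK sample (Tables 9.5-2 and 9.5-3, footnote b).** It is collected once all drug has been infused. If the line is flushed, "then draw the EOI PK sample within approximately 15 minutes after end of the flush". The EOI row has no clock time and points to this footnote.
- **Reason for that window (summary of key changes for Amendment 07, Section 9.5 entry).** It was widened from 5 to 15 minutes to leave time for the ECG.

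**The concern.** EOI on C1D1 and C3D1 meets the condition for the tolerance, because triplicate ECGs, vital signs and a PK sample all fall there. The tolerance does no harm predose, where concentration is not changing quickly. At EOI it does, because concentration rises steeply up to that moment. Fifteen minutes before the end of a 30-minute infusion, half the dose is still to be given.

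The current text therefore holds two timing rules for the same ECG. The ECG notes and footnote b imply this order: infusion ends, ECG, PK draw. The tolerance permits the ECG before the infusion ends. Only the first order gives the time-matched pairs that Section 9.1.3 calls for. If sites follow the second, ECGs taken at a lower concentration are paired with a concentration near the peak, and a direct effect on QTc would look smaller than it is. Part 1A is the only part with triplicate ECGs, so no other part can supply replacement pairs.

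**Working it through.** **Inputs.** Tolerance 15 minutes (text after Table 2-5); infusion T = 30 minutes (Table 7.3-1); three ECGs 5 minutes apart (Section 9.1.3); projected half-life 15 days (Section 3.2.1.2); plasma volume 40 mL/kg (Section 5.5.1.1); doses of about 0.03 and 3 mg/kg for 2 and 200 mg (Section 3.2.1.3).

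**1. The plan's own figure.** The visible text states no precision or power for the QTc evaluation. The one stated figure that bears on it is the projected Cmax in Section 3.2.1.3. Cmax = dose per kg / plasma volume:
- 2 mg: 0.03 mg/kg / 40 mL/kg = 0.75 µg/mL
- 200 mg: 3 mg/kg / 40 mL/kg = 75 µg/mL

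Both match the protocol.

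**2. Earliest permitted ECG times, if nominal EOI is the end of infusion.** 30 - 15 = 15 minutes. Taking the limit to bind the first reading, the triplicate falls at 15, 20 and 25 minutes.

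**3. Concentration at those times, C1D1.** Assume a constant-rate infusion and one compartment, with k = ln 2 / (15 × 24 × 60) per minute. The fraction of the EOI value is (1 - exp(-kt)) / (1 - exp(-kT)), in effect t/T because k is so small. This gives 0.500, 0.667 and 0.833, mean f = 0.667. At 200 mg that is 0.667 × 75 = 50 µg/mL at the ECGs, against 75 µg/mL in the paired sample.

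**4. C3D1, with carry-over.** Express the predose level c in units of the rise from one dose.
- Q4W, two earlier doses: r = 0.5^(28/15) = 0.274; c = r + r² = 0.349. Fraction = (0.667 + 0.349) / 1.349 = 0.753.
- Q2W, four earlier doses: r = 0.5^(14/15) = 0.524; c = r + r² + r³ + r⁴ = 1.017. Fraction = (0.667 + 1.017) / 2.017 = 0.835.

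**5. Effect on the slope.** Take the four pairs (predose and EOI, Cycles 1 and 3) at one dose level, equally weighted, with a direct linear effect of true slope 1. Recorded concentrations are 0, 1, c and 1 + c. Responses are 0, f, c and f + c. Least squares gives slope = (f + c²) / (1 + c²).
- Q4W: (0.667 + 0.122) / 1.122 = 0.703
- Q2W: (0.667 + 1.034) / 2.034 = 0.836

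The slope shortfall is therefore about 30% (Q4W) to 16% (Q2W).

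**6. Other readings.**
- ECGs between the end of infusion and a PK draw 15 minutes later: exp(-15k) = 0.9995, so the mismatch is under 0.1%. Three ECGs span 10 minutes and fit in that window.
- Nominal time is a PK draw 15 minutes after the flush: the earliest ECG is at the end of the flush, with the same negligible mismatch. A draw 5 minutes after the flush would allow an ECG 10 minutes before the flush ended.
- Shorter infusion, which Section 5.1.2 allows at low doses: at EOI minus 15 minutes the C1D1 fraction is (20 - 15)/20 = 25% for a 20-minute infusion and 0% for a 15-minute one.

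**The case against.** The best defence is that the plan already shows the order it wants. ECGs come before blood draws, the EOI PK sample waits until all drug is in, and Amendment 07 widened the PK window so that the ECG fits between the two. The tolerance exists to protect PK timing, is optional, and counts from a nominal time that is never defined for EOI. Anchored to a PK draw 15 minutes after the flush, it creates almost no mismatch. The analysis method cannot be seen either: part of Section 10.3 is not shown, and the SAP is still to be finalised. Early ECGs might be paired on actual times or flagged.

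Most of this stands. The intent is clear, and nothing shows that sites use the tolerance at EOI. It does not remove the conflict in the text. Footnote b refers to the nominal infusion duration and moves the PK sample if the infusion overruns, which favours reading EOI as the end of infusion. The PK-draw anchor helps only when the draw comes late in its window, and no minimum delay is set.

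**Conclusion.** The conflict is real and minor. As written, the tolerance lets the EOI triplicates in Part 1A be recorded during the infusion and paired with a post-infusion sample, contrary to Section 9.1.3 and to the sequence that the rest of the plan implies. The worst-case slope is about 0.70 (Q4W) to 0.84 (Q2W) of the true value. That rests on four assumptions: EOI means the end of a 30-minute infusion, every EOI triplicate starts the full 15 minutes early, the effect is direct and linear without lag, and recorded pairs are used as they stand. With partial use the bias is proportionally smaller.

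A reader might infer that the QTc pairs are in fact mid-infusion and that any effect will be understated by a quarter to a third. The documents do not support that. The rule says what is allowed, not what was done. The concentration shortfalls of 33% (C1D1) and 25% (C3D1 Q4W) leave out the Q2W schedule, where the C3D1 shortfall is about 16.5%. They are also not the slope bias, because predose pairs are unaffected and the C3D1 predose pair carries drug. With a lagged effect the calculation would not apply.

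**What to change.** - **Text after Table 2-5.** Add one sentence: the early-ECG tolerance does not apply to EOI triplicate ECGs, which are recorded after the infusion and flush have ended and before the EOI PK sample. This also settles the nominal time.
- **QTc analysis.** Pair on actual ECG, infusion-end and PK times. Flag EOI ECGs recorded before the end of infusion, and run a sensitivity analysis that excludes them. Apply the flag to data already collected: Section 3.2.1 reports Part 1A dosing up to 150 mg Q4W and 50 mg Q2W, and new wording cannot change those ECGs.
- **Infusion times.** Section 5.1.2 and Table 7.3-1 differ for low-dose cohorts and must be reconciled, since the mismatch depends on duration.

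The cost is one sentence, one data flag and one sensitivity analysis. No visit or procedure is added, because the EOI PK window already leaves room for the triplicate. ECGs already recorded can be flagged only if their actual times and the infusion end times were captured.
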